7.3.2. Spirometry

Spirometry measurements will be obtained using spirometry equipment that meets or exceeds the minimal performance recommendations of the ATS [Miller, 2005]. All sites will use standardized spirometry equipment provided by an external vendor.

All subjects will have spirometry performed at Screening to assess eligibility (see Section 7.2.2.1) and at Visits 2, 3, 4 and 5 during the treatment period.

For FEV_1 and FVC determinations, at least 3 acceptable spirometry efforts (with no more than 8) should be obtained. Acceptable spirometry efforts should have a satisfactory start of test and end of test (i.e. a plateau in the volume time curve) and be free from artifacts due to cough, early termination, poor effort, obstructed mouthpiece, equipment malfunction, or other reasons [Miller, 2005].

The largest FEV_1 and FVC from the 3 acceptable efforts should be recorded, even if they do not come from the same effort.

Spirometry for FEV_1 and FVC assessments that is not obtained as follows will be considered a protocol deviation:

- Started between 6:00AM and 11:00AM.
- After withholding albuterol/salbutamol (all visits) for ≥ 4 hours
- At Screening Visit 1, after wash out of medications as specified in the exclusion criteria in Section 5.2 (Concomitant Medications).
- At Screening Visit 1, before the morning dose of usual COPD medications
- At Visit 2 after discontinuing inhaled COPD medications and prior the first dose of study treatment
- At Visit 3, 4 and 5 after withholding the morning dose of study treatment.
- Pre dose assessment performed prior dosing.

Subjects should refrain from smoking for 1 hour prior to each pulmonary function test.

Trough FEV_1 measurements for UMC/VI or UMEC on Weeks 4, 12 and 24 (Visits 3, 4 and 5) should be performed 23 hours and 24 hours after the previous day's dose of study medication recorded in the eDiary. This will also provide trough FEV_1 measurements for the evening dose of salmeterol.

7.3.3. **Inspiratory capacity (IC)**

Inspiratory capacity (IC) is the volume of gas that can be taken into the lungs in a normal and full inhalation. Starting from the resting inspiratory position it is equal to the tidal volume plus the inspiratory reserve volume. IC has been widely used to assess static and dynamic hyperinflation in patients with COPD.

IC will be measured by spirometry **prior** to forced manoeuvres pre-dose at Visits 2 (30 and 5 min prior to dosing) and at trough at Visits 3, 4, and 5 (23 and 24 hrs post dosing on the previous day). For IC determination the average of at least three acceptable manoeuvres should be recorded. Subjects should be tested while sitting, relaxed and wearing a nose clip. They should be asked to breathe regularly for several breaths until the end-expiratory lung volume is stable (this usually requires at least three tidal manoeuvres) then urged to take a deep breath to Total Lung Capacity (TLC) with no hesitation.

Spirometry for IC determination done in conjunction with FEV₁ and FVC assessments that is not obtained as follows will be considered a protocol deviation:

- Started between 6:00AM and 11:00AM.
- After withholding albuterol/salbutamol (all visits) ≥ 4 hours
- At Visit 2 after discontinuation of run-in medication
- At Visit 3, 4 and 5 after withholding the morning dose of study drug

7.3.4. COPD Exacerbation

A mild exacerbation is defined as worsening of symptoms that require no treatment with antibiotics or steroids, and is self managed by the patient by an increase of inhaled rescue medications. A moderate COPD exacerbation is defined as worsening symptoms of COPD that require treatment with oral/systemic corticosteroids and/or antibiotics. A severe exacerbation is defined as worsening symptoms of COPD that require in-patient hospitalization or emergency room for longer than 24 hrs.

If a subject experiences a mild, moderate or severe COPD exacerbation, the COPD exacerbation page of the eCRF should be completed. COPD exacerbations should not be recorded as an AE, unless they meet the definition of a SAE. Details of COPD exacerbation identification, categorization and treatment guidelines are described in [Appendix 5](#).

Subjects who experience a mild exacerbation during the run-in period will not be withdrawn from the study. However, Subjects who experience moderate or severe exacerbation during the run-in period will be withdrawn from the study and will not be allowed to be re-screened.

Subjects who experience a mild, moderate or severe exacerbation during the treatment period, will **not** be withdrawn from the study unless the investigator or GSK medical monitor think it is best for the patient to withdraw from the study.

Signs and symptoms of COPD included on the electronic diary cards will not be considered AEs and will not be recorded in the eCRF.

The time period for collection of COPD exacerbations will be from the Pre-Screening (Visit 0) until completion of the follow-up contact. If a subject experiences a COPD exacerbation from the time the ICF is signed until randomization, summary information (yes/no status question) will be collected in the eCRF. COPD exacerbations after randomization through follow-up will be recorded on the COPD exacerbation page of the eCRF.

7.3.5. Clinically important deterioration (CID)

Clinically important deterioration (CID) is a composite endpoint defined as:

- A decrease of ≥ 100 mL from baseline in trough FEV₁

- A deterioration in HRQoL defined as ≥ 4 units increase from baseline in SGRQ
- The occurrence of an on-treatment moderate/severe COPD exacerbation

In addition, this study will explore CAT and TDI PROs as part of the composite endpoint.

7.3.6. Rescue albuterol/salbutamol use

Subjects will record the number of daily albuterol/salbutamol puffs they use in the eDiary. In addition, in some countries and selected sites the number of puffs will be collected through the eMDI device (Section [6.2](#))

7.3.7. Physical activity monitor (study subset)

Physical activity limitation is a common feature of COPD and its measures are highly related to the degree of disease severity [[Watz](#), 2009].

Reduced physical activity levels in COPD is associated with increased morbidity and mortality, sustained disability, depression, and social and physical isolation [[Shu-Yi](#), 2014; [Gimeno](#), 2014]

Improved activity has been identified as an important factor that may modify morbidity and mortality in COPD [[Moy](#), 2012].

The Actigraph GT9X physical activity monitor will be used to measure levels of activity. The activity monitor will be worn by up to approximately 150 subjects per treatment arm for 7 days from Screening (Visit 1), for 7 days from Randomisation (Visit 2), 7 days from Visit 3 (Week 4) and for 7 days prior to Week 24 (Visit 5).

There will be 4 assessment periods, including a screening assessment in order to provide a reliable estimate of habitual physical activity. Each subject will be given an activity monitor and instruction leaflet at the start of each assessment period. Further details of distribution, operation and retrieval of the monitors will be provided in the **SRM**.

7.4. Safety

Planned time points for all safety assessments are listed in the Time and Events Table (Section [7.1](#))

Safety endpoint includes:

- Incidence of adverse events

7.4.1. Adverse Events (AE) and Serious Adverse Events (SAEs)

The definitions of an AE or SAE can be found in [Appendix 4](#).

The investigator and their designees are responsible for detecting, documenting and reporting events that meet the definition of an AE or SAE.

7.4.1.1. Time period and Frequency for collecting AE and SAE information

- Any SAEs assessed as related to study participation (e.g., protocol-mandated procedures, invasive tests, or change in existing therapy) or related to a GSK product will be recorded from the time a subject consents to participate in the study up to and including any follow-up contact.
- AEs will be collected from the start of Study Treatment until the follow-up contact (see Section [7.4.1.3](#)), at the timepoints specified in the Time and Events Table (Section [7.1](#)).
- Medical occurrences that begin prior to the start of study treatment but after obtaining informed consent may be recorded on the Medical History/Current Medical Conditions section of the CRF.
- All SAEs will be recorded and reported to GSK within 24 hours, as indicated in ([Appendix 4](#), Section [12.4.6](#))
- Investigators are not obligated to actively seek AEs or SAEs in former study subjects. However, if the investigator learns of any SAE, including a death, at any time after a subject has been discharged from the study, and he/she considers the event reasonably related to the study treatment or study participation, the investigator must promptly notify GSK.

NOTE: The method of recording, evaluating and assessing causality of AEs and SAEs plus procedures for completing and transmitting SAE reports to GSK are provided in ([Appendix 4](#), Section [12.4.4](#) to Section [12.4.6](#))

7.4.1.2. Method of Detecting AEs and SAEs

Care will be taken not to introduce bias when detecting AEs and/or SAEs. Open-ended and non-leading verbal questioning of the subject is the preferred method to inquire about AE occurrence. Appropriate questions include:

- “How are you feeling?”
- “Have you had any (other) medical problems since your last visit/contact
- “Have you taken any new medicines, other than those provided in this study, since your last visit/contact?

7.4.1.3. Follow-up of AEs and SAEs

After the initial AE/SAE report, the investigator is required to proactively follow each subject at subsequent visits/contacts. All SAEs, and non-serious AEs of special interest (as defined in Section [4.6.1](#)) will be followed until resolution, until the condition stabilizes, until the event is otherwise explained, or until the subject is lost to follow-up (as defined in Section [5.5](#)).

7.4.1.4. Pneumonia Events

Investigators will be required to fill out a pneumonia event specific eCRF within one week of when the pneumonia AE/SAE(s) is first reported.

7.4.1.5. Cardiovascular and Death Events

For any cardiovascular events detailed in (Section 12.4.3) and all deaths, whether or not they are considered SAEs, specific Cardiovascular (CV) and Death sections of the CRF will be required to be completed. These sections include questions regarding cardiovascular (including sudden cardiac death) and non-cardiovascular death.

The CV CRFs are presented as queries in response to reporting of certain CV MedDRA terms. The CV information should be recorded in the specific cardiovascular section of the CRF within one week of receipt of a CV Event data query prompting its completion.

The Death CRF is provided immediately after the occurrence or outcome of death is reported. Initial and follow-up reports regarding death must be completed within one week of when the death is reported.

7.4.1.6. Disease-Related Events and/or Disease-Related Outcomes Not Qualifying as SAEs

The following disease related events (DREs) are common in subjects with COPD and can be serious/life threatening:

- COPD exacerbation

COPD exacerbations are associated with the disease to be studied and will not be recorded as AEs unless the exacerbation meets the definition of a 'serious' AE. Exacerbations that meet the definition of 'serious' AEs will be recorded on the appropriate eCRF section and should be reported to GSK for all subjects regardless of whether or not they are randomized to study medication. Signs and symptoms of COPD included on the electronic diary will not be considered AEs and will not be recorded in the eCRF

7.4.1.7. Regulatory Reporting Requirements for SAEs

Prompt notification by the investigator to GSK of SAEs related to study treatment (even for non- interventional post-marketing studies) is essential so that legal obligations and ethical responsibilities towards the safety of subjects and the safety of a product under clinical investigation are met.

GSK has a legal responsibility to notify both the local regulatory authority and other regulatory agencies about the safety of a product under clinical investigation. GSK will comply with country specific regulatory requirements relating to safety reporting to the regulatory authority, Institutional Review Board (IRB)/Independent Ethics Committee (IEC) and investigators.

Investigator safety reports are prepared for suspected unexpected serious adverse reactions according to local regulatory requirements and GSK policy and are forwarded to investigators as necessary.

An investigator who receives an investigator safety report describing a SAE(s) or other specific safety information (e.g., summary or listing of SAEs) from GSK will file it with the IB and will notify the IRB/IEC, if appropriate according to local requirements.

7.4.2. Pregnancy

- Details of all pregnancies in female subjects will be collected after the start of Screening and until the follow-up contact.
- If a pregnancy is reported then the investigator should inform GSK within 2 weeks of learning of the pregnancy and should follow the procedures outlined in [Appendix 7](#).

7.4.3. Medical Device Incidents (Including Malfunctions)

Procedures for documenting medical device incidents are provided in [Appendix 6](#).

7.4.4. Electrocardiogram (ECG)

A Single 12-lead ECG will be obtained at Screening using an ECG machine provided by the investigational site that automatically calculates the heart rate and measures PR, QRS, QT, and QTc intervals.

The 12-lead ECG measurement and rhythm strip (10 seconds) will be obtained before spirometry testing. ECG measurement should be obtained after subjects have rested for approximately 5 minutes then the subjects should be placed in the supine position for the ECG measurements. An ECG is only required at Screening Visit 1 for eligibility assessment only.

The investigator, a designated sub-investigator, or other appropriately trained site personnel will be responsible for performing and interpreting the 12-lead ECG at Screening Visit 1. The investigator must provide his/her dated signature on the original paper tracing, attesting to the authenticity of the ECG machine interpretation.

7.5. Genetics

Information regarding genetic research is included in [Appendix 3](#)

8. DATA MANAGEMENT

- For this study subject data will be entered into GSK defined CRFs, transmitted electronically to GSK or designee and combined with data provided from other sources in a validated data system.
- Management of clinical data will be performed in accordance with applicable GSK standards and data cleaning procedures to ensure the integrity of the data, e.g., removing errors and inconsistencies in the data.

- Adverse events and concomitant medications terms will be coded using MedDRA (Medical Dictionary for Regulatory Activities) and an internal validated medication dictionary, GSKDrug.
- CRFs (including queries and audit trails) will be retained by GSK, and copies will be sent to the investigator to maintain as the investigator copy. Subject initials will not be collected or transmitted to GSK according to GSK policy.

9. STATISTICAL CONSIDERATIONS AND DATA ANALYSES

9.1. Hypotheses

The primary purpose of this study is to demonstrate improvements in lung function for subjects treated with UMEC/VI compared with UMEC for 24 weeks.

The primary endpoint is change from baseline in trough FEV₁ at Week 24.

The null hypothesis is no difference between treatment groups ($H_0: \mu_T - \mu_S = 0$), with the alternative hypothesis that there is a difference between treatment groups ($H_1: \mu_T - \mu_S \neq 0$), where μ_T is the mean change from baseline for UMEC/VI and μ_S is the mean change from baseline for UMEC.

9.2. Sample Size Considerations

The primary endpoint is change from baseline in trough FEV₁ at Week 24. As an important aim of the study is to compare UMEC/VI, UMEC and salmeterol with respect to HRQoL the sample size has been calculated to provide sufficient power for the comparison of the primary and secondary endpoint TDI, at Week 24.

The sample size calculations use a two-sided 5% significance level and an estimate of between subject standard deviation for TDI of 2.94 units. The estimate of SD is based on DB2113373 [[Donohue](#), 2013], a study which consisted of treatment arms of UMEC/VI 62.5/25, UMEC 62.5 VI (Vilanterol) 25mcg and placebo and is the value at Day 168 in a subgroup of subjects who were ICS free at screening. Based on these data, 727 evaluable subjects per treatment arm will be required to provide 90% power to detect a statistically significant difference if the true difference is 0.5 units, $\frac{1}{2}$ the MCID, between UMEC/VI and UMEC. The smallest observed effect predicted to result in a statistically significant difference between treatment groups is 0.31 units.

With this number of evaluable subjects per arm, the study will have >99% power assuming a true treatment difference of 80mL between UMEC/VI and UMEC for trough FEV₁ at 24 weeks at the two-sided 5% significance level. This calculation uses a SD for trough FEV₁ of 240mL, based on prior results for trials comparing dual bronchodilators versus single bronchodilators ([Donohue](#), 2013; [Bateman](#), 2013). The smallest observed effect predicted to result in a statistically significant difference between treatment groups is 25mL.

In order to account for a 10% withdrawal rate, approximately 808 subjects per treatment arm will be randomised.

9.2.1. Sample Size Assumptions

9.2.2. Sample Size Sensitivity

The assumption of a SD of 2.94 units for the TDI total score is based on estimates from previous studies. The following table presents the power achieved with the proposed sample size of 727 randomised subjects per arm, should the assumption around the SD of the data change.

The actual assumptions used in the sample size calculation are shaded.

Endpoint	Between subject SD	Treatment Difference	Power
TDI	2.54	0.5	96%
	2.74	0.5	94%
	2.94	0.5	90%
	3.14	0.5	86%
	3.34	0.5	81%

9.2.3. Sample Size Re-estimation or Adjustment

No sample size re-estimation is planned for this study.

9.3. Data Analysis Considerations

9.3.1. Analysis Populations

Population	Definition / Criteria	Analyses Evaluated
All Subjects Enrolled (ASE)	
 All subjects for whom a record exists in the study database, including screen failures and any subject who was not screened but experienced an SAE between the date of informed consent and the planned date of the Screening visit. 	
 Subject Disposition Reasons for withdrawal prior to randomisation Inclusion, exclusion and randomisation criteria deviations SAEs for non-randomised

Population	Definition / Criteria	Analyses Evaluated
Intent-to-treat (ITT)	
 • All randomized subjects, excluding those who were randomized in error and received at least one dose of study medication. A subject who is recorded as a screen or run-in failure and also randomized will be considered to be randomized in error. Any other subject who receives a randomization number will be considered to have been randomized. • Displays will be based on the treatment to which the subject was randomized. 	
 • Study Population • Efficacy • Safety
Intent-to-treat ICS free (ITT ICS free)	
 • All subjects in the ITT Population who have not received ICS. 	
 • Study Population • Efficacy • Safety

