9.4. Key Elements of Analysis Plan

Treatment Comparisons

The primary treatment comparison of UMEC/VI with UMEC will be performed on the ITT population.

The other treatment comparisons of UMEC/VI and UMEC with Salmeterol will be performed on the ITT population and ITT ICS free population.

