9.4.2. Other Analyses

The MMRM analysis will be repeated for the ITT ICS free population. Estimated differences between UMEC/VI or UMEC and Salmeterol will be presented together with 95% confidence intervals (CIs) for the difference and p-values.

Secondary and other efficacy endpoints and treatment comparisons will be adjusted for multiplicity as per Section [9.4.1](#).

Full details of the analyses to be performed on the other efficacy endpoints will be given in the RAP.

Safety Analyses

Adverse events (AEs) will be coded using the standard GSK dictionary, Medical

Dictionary for Regulatory Activities (MedDRA), and grouped by body system. The number and percentage of subjects experiencing at least one AE of any type, AEs within each body system and AEs within each preferred term will be presented for each treatment group. Separate summaries will be provided for all AEs, drug related AEs, fatal AEs, non-fatal SAEs, AESIs and AEs leading to withdrawal.

Deaths and SAEs will be documented in case narrative format.

Full details of the analyses to be performed on all safety endpoints will be given in the RAP.

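### The ITT definition removes subjects randomized in error who were dosed, so they drop out of the treatment-group efficacy and adverse event summaries

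*Protocol*

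**What the plan says.** Section 9.3.1 of the protocol gives the ITT population as "All randomized subjects, excluding those who were randomized in error and received at least one dose of study medication". It then explains the error category: "A subject who is recorded as a screen or run-in failure and also randomized will be considered to be randomized in error". Everyone else with a number counts: "Any other subject who receives a randomization number will be considered to have been randomized". Grouping follows allocation: "Displays will be based on the treatment to which the subject was randomized".

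The same table assigns ITT to study population, efficacy and safety. The other set listed for safety, ITT ICS free, is "All subjects in the ITT Population who have not received ICS", so it cannot hold anyone ITT leaves out. The All Subjects Enrolled set covers everyone with a database record, but its one safety use is "SAEs for non-randomised" subjects. No separate set of treated subjects is defined.

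Section 9.4 states that "The primary treatment comparison of UMEC/VI with UMEC will be performed on the ITT population". Section 9.4.2 plans adverse event counts by treatment group and adds: "Separate summaries will be provided for all AEs, drug related AEs, fatal AEs, non-fatal SAEs, AESIs and AEs leading to withdrawal". The September 2016 version of the protocol in the same file has the same ITT wording.

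**The concern.** Populations of this kind normally drop subjects who entered by mistake and never took drug, because they carry no information on treatment. This sentence attaches the dosing condition so that mistaken entrants who did take drug are the ones removed. A subject exposed to study medication for any length of time would then contribute neither to the primary comparison nor to the adverse event tables by arm.

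Two things are at stake. The first is completeness of safety reporting: a treated subject's non-serious adverse events, drug-related events, events of special interest and events leading to withdrawal would have no table to appear in. The second is that the membership of the primary analysis set is not uniquely fixed, because the sentence admits two readings that give different sets.

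**Working it through.** **Membership under both readings.** Reading A takes the sentence literally: exclude anyone who is both in error and dosed. Reading B takes dosing as a second entry requirement: randomized, not in error, and dosed.

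| Randomized in error | Dosed | Reading A | Reading B |
|---|---|---|---|
| No | No | in | out |
| No | Yes | in | in |
| Yes | No | in | out |
| Yes | Yes | **out** | **out** |

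The last row is the same in both columns, so the loss of the in-error, dosed subject does not depend on grammar. The readings differ in both undosed rows, so the text does not settle whether a dose is required. Under A, an in-error subject is kept if undosed and removed if dosed.

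**Where such a subject could otherwise be counted.**
- ITT ICS free: no, because it is a subset of ITT.
- All Subjects Enrolled: yes for disposition and criteria deviations. For safety, only the listing of SAEs in non-randomised subjects applies. Section 9.3.1 says that any *other* subject with a number counts as randomized, so an in-error subject might fall into that listing, but the text does not say so.
- Non-serious adverse events: no set is assigned.

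**Consistency of the trigger.** Section 5.4 defines screening failures as not entering run-in, and run-in failures as entering run-in but not being allocated to an arm. A randomized subject fits neither definition. The category in section 9.3.1 therefore exists only where a subject's records conflict.

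**The plan's sample size, reproduced first (section 9.2).** Inputs: TDI difference 0.5, SD 2.94, two-sided 5%, power 90%.

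n per arm = 2 × (1.960 + 1.282)² × 2.94² / 0.5² ≈ 727, as stated. Allowing for 10% withdrawal, 727 / 0.9 = 807.8, rounded up to 808. Then 3 × 808 = 2424 randomized and 3 × 727 = 2181 evaluable, also as stated.

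**Effect of removing a fraction f.** The protocol gives no rate, so f is an assumption. Affected subjects = 2424 × f; evaluable per arm = 727 × (1 − f). Power is for TDI as above and for trough FEV1 with 80 mL and SD 240 mL (section 9.2). The last column is 1 − 0.99^m, where m is the number affected: the chance that the removed group holds at least one subject with an event of assumed 1% incidence.

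| f (assumed) | Affected | Evaluable per arm | TDI power | FEV1 power | At least one 1% event |
|---|---|---|---|---|---|
| 0.25% | 6 | 725.2 | 0.8995 | >99.9% | 6% |
| 1% | 24 | 719.7 | 0.8973 | >99.9% | 21% |
| 5% | 121 | 690.6 | 0.8850 | >99.9% | 70% |

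The table shows that efficacy power barely moves. The consequence lies in what the safety tables omit, and its size depends wholly on the unknown f.

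**The case against.** The strongest case on the other side is that little of practical weight follows, and much of it stands.

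- *Serious events.* A reader might infer that serious events in these subjects are lost. The protocol does not support that. Section 7.4.1.1 requires all SAEs to be recorded and sent to the sponsor within 24 hours, section 7.4.1.6 requires serious exacerbations to be reported whether or not the subject was randomized, and section 9.4.2 promises narratives for deaths and SAEs without limiting them to ITT. What is missing is their place in the summaries by arm.
- *Numbers.* The category is narrow. An ineligible subject who carries a randomization number but no failure record stays in ITT, and section 5.4 means that a conflicting record is needed. Any percentage is assumed, and only the dosed part of the category is affected. The number may be zero or a handful.
- *Bias.* A reader might infer a selective exclusion after randomization. No section says a failure record may be entered after allocation, the failure concerns screening or run-in status, and the trial is double-blind. Differential exclusion by arm is not shown. It is equally true that no section requires the record to precede dosing.
- *Treatment received.* A reader might infer that events will be credited to the wrong drug because displays follow allocation. Drug is allocated centrally (section 6.3), no dispensing error rate is given, and section 9.4.2 leaves full safety details to the analysis plan, which is not shown. This is a preference and not an error.

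What the objection does not reach is the stated definition itself. The protocol fixes it and assigns it to efficacy and safety, and on either reading it removes exposed subjects.

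**Conclusion.** The point holds in limited form. As written, the ITT definition excludes every subject who was randomized in error and took study medication, and it leaves open whether undosed subjects are in. Because ITT and its subset serve the by-treatment safety displays, those exposed subjects leave both the efficacy and the adverse event summaries, and their non-serious events have no stated home. They remain in the enrolled set for disposition and deviations, and their serious events are still reported and narrated.

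The effect on primary inference is negligible across the assumed range. The number of subjects is not given and is probably small. The finding rests on the text of section 9.3.1 and not on any assumed rate. Severity: should be fixed. It does not threaten the trial's main conclusion, but it is a plain drafting fault in the primary and safety sets, best corrected before unblinding so that the change cannot look data-driven.

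**What to change.** Separate the two conditions in section 9.3.1.

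1. Define ITT as all randomized subjects, analysed as randomized, excluding only those randomized in error who received no dose. If the sponsor also means to require a dose for ITT, state that as its own condition, since it would remove correctly randomized subjects who were never dosed.
2. State that adverse event displays use every subject who received at least one dose, whether or not recorded as randomized in error, and state the treatment grouping used.
3. Reconcile the term for randomization in error with section 5.4, where a run-in failure is by definition not randomized, and say which record decides the matter.

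The cost is a short wording change and one programming flag. The sample size, visits and data collection are unchanged.
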